## **6.1.2. General Considerations for Analyses during the Blinded Treatment Dosing Period (Period 2)**

### **6.1.2.1. Intent-to-Treat Population and Safety Population**

Period 2 starts at the first injection of study treatment at Week 0 (Visit 2) and ends on the date of Week 52 (Visit 15) or the early termination visit (ETV; between Weeks 0 and 52). For patients who were deemed as inadequate responders by their investigators and were treated with biologic rescue of ixekizumab 80 mg Q2W, only data up to the time of initiation of biologic rescue of ixekizumab 80 mg Q2W will be included in the Period 2 analyses using the ITT and Safety Populations. These patients will be considered nonresponders to categorical assessment per the nonresponder imputation (NRI) method after initiation of biologic rescue with ixekizumab 80 mg Q2W. Data collected after biologic rescue therapy has started will be summarized separately for the IR Population (Section 6.1.2.2).

Baseline for ITT and Safety Populations will be defined as the last available value before the first injection for efficacy, health outcomes, and safety analyses. In most cases, this will be the measure recorded at Week 0 (Visit 2). For efficacy measures, if the patient does not take any injection, the last available value on or prior to randomization date will be used. Change from baseline (CFB) will be calculated as the visit value of interest minus the baseline value. For safety analyses using a baseline period, the baseline period is defined as the time from Visit 1 to the date/time of the first injection.

Comparisons between each initially randomized ixekizumab treatment group (80 mg Q2W or 80 mg Q4W) and initially randomized placebo will be performed for all analyses in Period 2.

The randomization to treatment groups is stratified by country and screening MRI/CRP status (positive MRI and elevated CRP; positive MRI and nonelevated CRP; negative MRI and elevated CRP) as described in Protocol Section 6.2. The countries will be categorized into geographic regions for analysis. Geographic regions are defined in Table RHBX.6.3. Unless otherwise specified, the statistical analysis models will adjust for geographic region and screening MRI/CRP status.

Screening MRI and CRP status included in all the analysis models for Period 2 is determined based on the MRI readings and central lab CRP values obtained at screening visit (Visit 1).

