### 6.3.1. Nonresponder Imputation

Analysis of categorical efficacy and health outcome variables will be assessed using a nonresponder imputation (NRI) method. Patients will be considered nonresponders for the NRI analysis if they do not meet the clinical response criteria or have missing clinical response data at the primary analysis time points. All nonresponders at Week 16 (Visit 8), as well as all patients who discontinue study treatment at any time prior to Week 16 for any reason, will be defined as nonresponders for the NRI analysis at Week 16. Similarly, all nonresponders at Week 52 (Visit 15), as well as patients who discontinue study treatment at any time prior to Week 52 for any reason, will be defined as nonresponders for the NRI analysis at Week 52. Patients who are deemed as inadequate responders by the investigator on or after Week 16 but remain on initially assigned blinded study treatment and only have modifications in concomitant medications will not influence whether or not a patient would be considered a nonresponder. Patients who stopped originally assigned blinded study treatment and use rescue ixekizumab 80 mg Q2W will be analyzed as nonresponders for the Week 52 analysis. They will be considered as nonresponders after the time of initiation of biologic rescue of ixekizumab 80 mg Q2W.

Randomized patients without at least 1 postbaseline observation will also be defined as nonresponders for the NRI analysis.

The NRI may be applied at any time point specified for analysis.

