**Table RHBX.6.5. Description of Primary and Secondary Efficacy Analyses**

Measure	Variable	Analysis Method (Sections 6.1 and 6.3)	Population (Section 6.1.1)	Comparison/Time Point	Analysis Type
ASAS40	ASAS40 – Primary	Logistic regression analysis with NRI	ITT Population	IXE80Q2W & IXE80Q4W vs. placebo at Week 16	Primary analysis is logistic regression analysis with NRI for ITT Population comparing IXE80Q2W & IXE80Q4W vs. placebo at Week 16 (Section 6.10.1).
		Logistic regression analysis with NRI	ITT Population	IXE80Q2W & IXE80Q4W vs. placebo at Week 52	Primary analysis is logistic regression analysis with NRI for ITT Population comparing IXE80Q2W & IXE80Q4W vs. placebo at Week 52 (Section 6.10.1).
		Logistic regression analysis with NRI	ITT Population	IXE80Q2W & IXE80Q4W vs. placebo at all other postbaseline visits in Period 2	Additional analyses of primary outcome (Section 6.10.3).
		Logistic regression analysis with NRI	Per-Protocol Set (PPS)	IXE80Q2W & IXE80Q4W vs. placebo at Weeks 16 and 52	Additional analyses of primary outcome (Section 6.10.3).
		Categorical MMRM	ITT Population	IXE80Q2W & IXE80Q4W vs. placebo at Weeks 16 and 52 and all other postbaseline visits in Period 2	Additional analysis of primary outcome (Section 6.10.3).
		Fisher’s exact test with NRI	ITT Population	IXE80Q2W & IXE80Q4W vs. placebo at Weeks 16 and 52 and all other postbaseline visits in Period 2	Additional analyses of primary outcome (Section 6.10.3).
		Logistic regression analysis with NRI	ITT Population	IXE80Q2W & IXE80Q4W Starting Dose 160 mg and 80 mg during Period 2	Other secondary efficacy analyses for primary outcome (Section 6.10.4).
		pMI	ITT Population	IXE80Q2W & IXE80Q4W vs. placebo at Weeks 16 and 52	Sensitivity analyses (Section 6.10.5.1)
		Tipping point analysis	ITT Population	IXE80Q2W & IXE80Q4W vs. placebo at Weeks 16 and 52	Sensitivity analyses (Section 6.10.5.2)
		Subgroup analyses	ITT Population	IXE80Q2W & IXE80Q4W vs. placebo at Weeks 16 and 52	Subgroup analyses (Section 6.15.1)

Measure	Variable	Analysis Method (Sections 6.1 and 6.3)	Population (Section 6.1.1)	Comparison/Time Point	Analysis Type
		Descriptive statistics of ASAS40 response rate	IR Population	Period 2 post initiation of biologic rescue of ixekizumab 80 mg Q2W	Exploratory analyses (Section 6.10.6.1)

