### **6.10.6. Exploratory Analyses**

#### **6.10.6.1. Exploratory Analyses Post Biologic Rescue for Inadequate Responders**

For inadequate responders who initiated biologic rescue of ixekizumab 80 mg Q2W, summary statistics will be provided for categorical measures (ASAS40/20, BASDAI50, ASDAS <2.1, ASDAS clinical important improvement and major improvement) and continuous measures (CRP, BASFI, BASDAI, SF-36 PCS) to describe the treatment response post biologic rescue. For patients who further initiated other biologic rescues (such as TNF-i), a listing of ASAS40 and its domains, BASDAI score and CRP value will be produced. The length of exposure on initially randomized therapy, and biologic rescue of ixekizumab 80 mg Q2W will be summarized separately for the IR Population.

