**Table RHBX.6.10. Baseline and Postbaseline Definition for Immunogenicity Analyses in Period 2**

[figure not shown]
Analysis Purpose	Analysis Population	Treatment Group	Baseline Definition	Postbaseline Definition
Incidence of TE-ADA during Week 0-16	Safety Population	Group 1: PBO IXE 80mg Q4W IXE 80mg Q2W Total Ixe	Last non-missing observation on, or prior to the date of the first injection of study drug at Week 0 (before drug administration)	Week 0-16
Incidence of TE-ADA during Week 0 -52 while patients on Ixekizumab exposure	All Ixekizumab Exposure Safety Population a	Group 2: IXE 80mg Q2W – Q2W b IXE 80mg Q4W – Q4W c PBO - IXE 80mg Q2W d IXE 80mg Q4W – Q2W e All IXE 80mg Q2W f	Last non-missing observation on, or prior to the date of the first injection of ixekizumab, that is, PBO – ixe 80mg Q2W, baseline is before ixekizumab 80mg Q2W rescue. For other groups, it is Week 0	Time period between the first ixekizumab injection to the last visit. For patients who may take other biologic rescues (e.g. TNFi), the postbaseline period ends prior to the start of other biologic therapy.

Abbreviations: IXE = ixekizumab; PBO = placebo; Q2W = every 2 weeks; Q4W = every 4 weeks; TE-ADA = treatment-emergent anti-drug antibody; TFFi = tumor necrosis factor inhibitor.

- a defined as all patients who received at least one dose of ixekizumab during the study.
- b includes patients with only ixekizumab 80mg Q2W exposure, regardless of whether patients were rescued by ixekzimab 80mg Q2W
- c Includes patients with only ixekizumab 80mg Q4W exposure. Patients who were rescued by ixekizuamb 80mg Q2W are not included.
- d Includes patients who were originally assigned to placebo and were later on rescued by ixekizumab 80mg Q2W.
- e Includes patients who were originally assigned to ixekizumab 80mg Q4W and were later on rescued by Ixekizumab 80mg Q2W.
- f includes groups 1 and 3.

- **baseline ADA positive (preexisting antibody):** ADA detected in a sample collected at baseline.
- **baseline ADA-negative:** ADA is not detected in a sample collected at baseline.
- **treatment-emergent anti-drug antibody (TE-ADA) positive:** a) a patient with a  $\geq 4$ -fold increase over a positive baseline antibody titer (Tier 3); or b) for a negative baseline titer, a patient with an increase from the baseline to a level of  $\geq 1:10$ .

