### **6.13.8.2.2. Analyses of ADA Effects on Efficacy**

Efficacy analyses for Period 2 will be conducted on all evaluable patients within the safety populations n for Blinded Treatment Dosing Period for Groups 1 and 2, separately. Groups 1 and 2 are illustrated in [Table RHBX.6.10](#).

Assessment of Spondyloarthritis International Society 40 and ASDAS <2.1 (for patients with baseline ASDAS  $\geq$ 2.1) at Weeks 16 with NRI will be summarized by the TE-ADA status groups as described in Section [6.13.8.2.1](#) for the Safety Population.

A logistic regression model with treatment group, TE-ADA status group (excluding patients in the TE-ADA inconclusive category for TE-ADA, excluding TE-ADA positive and co-occurring NAb inconclusive subgroups for NAb) and the interaction of treatment group-by-TE-ADA status group included as factors will be used to test the interaction of treatment group -by-TE-ADA status group during Period 2 at Week 16. The p-value associated with the interaction term will be used to assess if the treatment effect is consistent across the TE-ADA status groups. When the interaction term is statistically significant, the association between responder status and treatment depends, in some manner, on the TE-ADA status group. The interaction will be tested at the 10% significance level. Treatment differences will be evaluated within each subgroup using Fisher's exact test regardless of whether the interaction is statistically significant.

Assessment of Spondyloarthritis International Society 40 and ASDAS <2.1 (for patients with baseline ASDAS  $\geq$ 2.1) at Weeks 52 with NRI will be summarized by the TE-ADA status groups as described in Section [6.13.8.2.1](#) for the All Ixekizumab Exposures Safety Population. No statistical testing will be performed.

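### Read literally, the SAP's Week 52 efficacy-by-antibody summary makes both rescue-defined rows 0/n and starts time to antibody at a placebo injection for rescued placebo patients; other SAP passages conflict with both

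*SAP*

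**What the plan says.** **Week 52 response by antibody status.** SAP 6.13.8.2.2 plans that ASAS40 and ASDAS <2.1 (the latter in patients with baseline ASDAS of at least 2.1) "at Weeks 52 with NRI will be summarized by the TE-ADA status groups as described in Section" 6.13.8.2.1. The population is the All Ixekizumab Exposures Safety Population, laid out as Group 2 of Table RHBX.6.10, and no testing is planned.

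**Row membership (Table RHBX.6.10).** For the placebo-to-Q2W row, note d reads "Includes patients who were originally assigned to placebo and were later on rescued by ixekizumab 80mg Q2W". For the Q4W-to-Q2W row, note e reads "Includes patients who were originally assigned to ixekizumab 80mg Q4W and were later on rescued by Ixekizumab 80mg Q2W". The Q2W-Q2W row takes everyone exposed only to Q2W, "regardless of whether patients were rescued by ixekzimab 80mg Q2W". Note f builds the pooled All IXE Q2W row from the first and third listed groups, which are Q2W-Q2W and placebo-to-Q2W.

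**The imputation rule.** SAP 6.3.1 says that patients who stop their assigned treatment and "use rescue ixekizumab 80 mg Q2W will be analyzed as nonresponders for the Week 52 analysis". It names no population. SAP 6.1.2.1 states the same consequence directly after limiting data to the pre-rescue period in "Period 2 analyses using the ITT and Safety Populations".

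**Time to antibody.** The formula in SAP 6.13.8.2.1 runs from the first injection of study treatment. The opening paragraph of that section leaves out time on placebo. Table RHBX.6.10 sets the baseline of placebo-to-Q2W patients before rescue and starts their postbaseline period at the first ixekizumab injection.

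**The concern.** Efficacy at Week 52 by antibody status is a listed secondary objective (SAP Section 4). A row whose members all had rescue, under a rule that makes rescue a nonresponse, carries no information about antibodies and response: it is zero whatever happens on ixekizumab. The pooled Q2W row then reports failure on placebo as if it were failure on ixekizumab.

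For time to antibody, weeks without any drug would count as weeks at risk of developing antibodies to it. Medians and Kaplan-Meier curves would show a delay produced by the clock. Censoring times for placebo-to-Q2W patients would be stretched in the same way.

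**Working it through.** The plan states no figure for these summaries, so there is none to reproduce. The check traces the rules.

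**1. The SAP 6.3.1 rule applied to each Group 2 row**

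| Row | Members | Week 52 result read literally |
|---|---|---|
| Q2W-Q2W | Q2W exposure only, rescued or not (note b) | Rescued members are nonresponders |
| Q4W-Q4W | Q4W only, rescued patients excluded (note c) | Rescue clause has no effect |
| Placebo to Q2W | Rescued placebo patients only (note d) | 0/n |
| Q4W to Q2W | Rescued Q4W patients only (note e) | 0/n |
| All IXE Q2W | Q2W-Q2W plus placebo to Q2W (note f) | Numerator from Q2W-Q2W only, denominator from both |

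The two 0/n results hold in every antibody category and for both endpoints.

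**2. Size of the dilution (illustration)**

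Inputs: 100 patients in Q2W-Q2W and a 40% response, both taken from the Week 52 power table (SAP Table RHBX.5.1). The number of rescued, evaluable placebo patients, n, is assumed to be 20, 40 or 60.

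Pooled rate = 40 / (100 + n):
- n = 20: 40/120 = 33.3%
- n = 40: 40/140 = 28.6%
- n = 60: 40/160 = 25.0%

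**3. Antibody contrast in the pooled row**

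Let antibody incidence be p1 in Q2W-Q2W and p2 in placebo-to-Q2W, with 40% response in both antibody strata of Q2W-Q2W (no true antibody effect).
- Antibody-positive rate = 40·p1 / (100·p1 + n·p2)
- Antibody-negative rate = 40·(1 − p1) / (100·(1 − p1) + n·(1 − p2))

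If p1 = p2, both reduce to 40/(100 + n) and the difference is zero. If they differ, a difference appears, and its sign follows the sign of p1 − p2. The documents give neither incidence. Equality is not assured. The Schedule of Activities (Protocol Appendix 2) gives Q2W-Q2W patients 10 samples after the first dose (Weeks 1, 2, 4, 8, 12, 16, 24, 28, 36, 52). Placebo-to-Q2W patients have 4 if rescued at Week 16 or 20, falling to 1 if rescued at Week 36 or 44.

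**4. Time to antibody**

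The formula is (days from origin + 1)/7, and rescue is allowed from Week 16 to Week 44 (Protocol 6.1). For a placebo patient whose first scheduled sample after rescue is positive:

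| Rescue week | Next sample week | Weeks as written | Weeks from first ixekizumab |
|---|---|---|---|
| 16 | 24 | 24.1 | 8.1 |
| 20 | 24 | 24.1 | 4.1 |
| 24 | 28 | 28.1 | 4.1 |
| 28 | 36 | 36.1 | 8.1 |
| 32 | 36 | 36.1 | 4.1 |
| 36 | 52 | 52.1 | 16.1 |
| 44 | 52 | 52.1 | 8.1 |

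The excess always equals the rescue week, so it is 16 to 44 weeks, give or take visit windows. Ixekizumab exposure by Week 52 is 52 − 16 = 36 weeks down to 52 − 44 = 8 weeks.

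**The case against.** A fair reader can say that the rescue clause was never meant for Group 2. Protocol 9.2.1 explains why post-rescue data are set aside: so that benefit from rescue is not credited to the randomized arm. That reason does not apply to a population defined by ixekizumab exposure. SAP 6.1.2.1 can be read as confining the clause to the ITT and Safety Populations. The SAP also reports response after rescue elsewhere without NRI: Table RHBX.6.5 lists "Descriptive statistics of ASAS40 response rate" for the Inadequate Responder Population, and 6.10.6.1 gives statistics "to describe the treatment response post biologic rescue".

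This stands to the extent that 0/n is the literal result and not a certain one. It does not settle the text. Section 6.3.1 has no population limit, 6.13.8.2.2 names NRI, and no other NRI rule exists. Where the SAP wants a different rule after rescue, it writes one: 6.3.2 has a separate paragraph on carrying observations forward in the Inadequate Responder Population.

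On timing, the opening paragraph of 6.13.8.2.1 already excludes placebo time, and the formula is correct for the Week 0 to 16 Safety Population that shares it. A reader might infer that the sponsor planned a placebo origin. The documents show only an explicit formula that contradicts its own section.

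The harm is also limited. The component rows are separate groups in Table RHBX.6.10, so a 0/n row would be conspicuous and Q2W-Q2W would be visible undiluted. The time-to-antibody displays are produced only if data suffice.

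**Conclusion.** The point holds as a conflict between passages whose literal reading gives wrong descriptive results. Under that reading both rescue-defined rows are 0/n, and rescued placebo patients enter the pooled Q2W row as nonresponders. The formula adds about 16 to 44 weeks to time to antibody in placebo-to-Q2W patients. The fall from 40% to between 33.3% and 25.0% is an illustration; it rests on 100 evaluable patients in Q2W-Q2W and on 20 to 60 rescued placebo patients.

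Two stronger inferences are not supported. A reader might infer that the pooled row will show a spurious antibody effect in a known direction. Its size and sign depend on incidences that the documents do not give, and it is zero if they are equal. A reader might also infer that efficacy conclusions are at risk. They are not: the Week 16 antibody interaction test and all primary and major secondary tests are unaffected. Severity is minor to moderate.

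**What to change.** 1. In SAP 6.13.8.2.1, for the All Ixekizumab Exposures population, set the time origin to the date of the first ixekizumab injection. Leave the Week 0 to 16 Safety Population formula as it is.
2. In SAP 6.13.8.2.2, state that for the Group 2 Week 52 summary the rescue clause of 6.3.1 applies in no row: not in placebo-to-Q2W, not in Q4W-to-Q2W, and not to rescued patients within Q2W-Q2W. Use observed response against the Week 0 baseline, as 6.1.2.2 already does for efficacy after rescue. Count missing data, ixekizumab discontinuation or start of another biologic as nonresponse. All rows and the pooled row then share one definition. If a rate with rescue counted as failure is also wanted for patients randomized to ixekizumab, show it separately and label it.
3. Add a footnote that rescued placebo patients have only about 8 to 36 weeks of ixekizumab exposure at Week 52.

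The cost is a few SAP sentences and one footnote, plus a labelled column if the second rate is shown. No new data are needed and no confirmatory test changes.

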### **6.13.8.2.3. Analyses of Treatment-Emergent ADA on Specific Adverse Events**

The analyses of TE-ADA effects on safety will be conducted on all immunogenicity evaluable patients for the All Ixekizumab Exposures Safety Population for the Blinded Treatment Dosing Period (Period 2 Week 0 to 52) when patients are on ixekizumab, including open label rescue with ixekizumab 80 mg Q2W (time period when patients are on placebo will be excluded). All patients will be analyzed in one group.

Adverse events of special interest of allergic reaction/hypersensitivity (anaphylaxis and non-anaphylaxis) and of injection-site reactions will be included in an assessment of AE to TE-ADA over time. Timing of an AE will be taken to be the reported AE start date.

For each TE-ADA status dichotomous variable (as defined in [Table RHBX.6.11](#)), patients will be categorized according to whether they were (i) always in lesser-TE-ADA status postbaseline or (ii) at some point postbaseline, were in greater-TE-ADA status. For each AESI, within the time-varying TE-ADA status groups, a summary will be provided of the number of patients who had no event, events only while in lesser-TE-ADA status for group (i), or – for group (ii) – at least 1 event while in greater-TE-ADA status.

Additionally, summaries will be provided of the total number of AESI events (with unique start dates) by time-varying TE-ADA status groups at the event date. The summaries will aggregate

time respectively in greater-TE-ADA status and in lesser-TE-ADA status, along with the event rates (rates per 100 patient-years) relative to those aggregate times.

By-patient listings will be provided of patients with TE-ADA who experience a treatment-emergent allergic reaction/hypersensitivity reaction or an injection site reaction.

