**Table RHBX.6.11. TE-ADA Status Dichotomous Variables for AE Analysis**

TE-ADA Status Dichotomous Variable	Greater-TE-ADA Status	Lesser-TE-ADA Status
TE-ADA positive	TE-ADA positive	not TE-ADA positive
TE-ADA moderate-to-high	TE-ADA positive with moderate titer or high titer	not TE-ADA positive, or TE-ADA positive with low titer
TE-ADA high status	TE-ADA positive with high titer	not TE-ADA positive, or TE-ADA positive with low or moderate titer

Abbreviations: AE = adverse event; TE-ADA = treatment-emergent anti-drug antibody.

Note: For purpose of this analysis, TE-ADA Inconclusive is taken to be “not TE-ADA positive.”

Note: A TE-ADA low is defined as a TE-ADA positive with a titer value <1:160; a TE-ADA moderate is defined as a TE-ADA positive with a titer value  $\geq$ 1:160 and <1:1,280; and a TE-ADA high is defined as a TE-ADA positive with a titer value  $\geq$ 1:1,280.

For each TE-ADA status dichotomous variable, a time-varying TE-ADA status will be computed. At time  $t$ , the TE-ADA status is taken to be the highest of the TE-ADA values bracketing time  $t$ . More formally, the TE-ADA status at time  $t$  is given by the greater of (a) the TE-ADA status at the most-recent postbaseline measurement prior to  $t$ , and (b) the TE-ADA status at the first TE-ADA postbaseline measurement at or after time  $t$ . In this computation, “greater” is given by the greater-TE-ADA status of Table RHBX.6.11. If there is no value satisfying criterion (a), then the value (b) is used. Similarly, if there is no value (b), then the value (a) is used.

For each TE-ADA status dichotomous variable, patients will be categorized according to whether they were (i) always in lesser-TE-ADA status postbaseline or (ii) at some point postbaseline, were in greater-TE-ADA status.

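### Hypersensitivity and injection-site event rates by antibody status are not split by time on ixekizumab, so they can differ in either direction with no antibody effect

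*SAP*

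**What the plan says.** SAP 6.13.8.2.3 covers the All Ixekizumab Exposures Safety Population over Weeks 0 to 52, including time on ixekizumab rescue. It states: "All patients will be analyzed in one group". One of its summaries counts "the total number of AESI events (with unique start dates) by time-varying TE-ADA status groups at the event date" and aggregates the time spent in each status, "along with the event rates (rates per 100 patient-years) relative to those aggregate times". No ratio, test or adjustment for time on drug is specified.

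The text around Table RHBX.6.11 fixes status at any time t: "the TE-ADA status is taken to be the highest of the TE-ADA values bracketing time" t. Before the first postbaseline sample the rule looks forward: "If there is no value satisfying criterion (a), then the value (b) is used". Inconclusive results count as not positive ("For purpose of this analysis, TE-ADA Inconclusive is taken to be" so). The definition under Table RHBX.6.10 needs a postbaseline rise in titer: "for a negative baseline titer, a patient with an increase from the baseline to a level of" at least 1:10. For placebo patients who are rescued, that table resets baseline to just before the first ixekizumab dose.

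The nearest time split is in SAP 6.13.3.1, which adds a Week 0 to 16 summary for these event types. It is by treatment group, not by TE-ADA status. Protocol 9.7.3 describes the purpose as comparing events in TE-ADA positive and negative patients, and provides for both persistent and transient positivity.

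**The concern.** A crude rate over aggregate time is a fair basis for comparison only if the two kinds of time are alike in everything else that drives the event. Here they need not be. TE-ADA develops after exposure starts, so the mix of early and late weeks on drug will usually differ between greater- and lesser-status time. Injection-site and hypersensitivity reactions may plausibly be more frequent after the first injections than later, although the documents do not say so. If they are, the two rates will differ for reasons unrelated to antibodies.

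At stake is how a safety question in the protocol is read. The output is descriptive, but two rates per 100 patient-years printed side by side will be taken as a comparison. A reader could be falsely reassured, or see a signal that is not there.

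**Working it through.** The SAP states no figure for this analysis, so there is none to reproduce. The check is whether the planned estimator returns 1 when the true antibody effect is exactly 1.

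**Inputs from the documents.** Antibody samples at Weeks 0, 1, 2, 4, 8, 12, 16, 24, 28, 36 and 52 (Protocol Appendix 2), and the SAP status rule: the higher of the two bracketing samples, or the first postbaseline sample if there is none before.

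**Assumptions, not in the documents.** 10% or 30% of patients become TE-ADA positive. Median onset is 2 to 16 weeks. Positivity persists or lasts 12 weeks. The event rate in an early window is H times the later rate.

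**Formula.** If a share p+ of greater-status time and p− of lesser-status time falls in the early window, then with no antibody effect

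crude ratio = [1 + (H − 1)p+] / [1 + (H − 1)p−].

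The shares come from applying the status rule to 4000 simulated patients per scenario. For a 4-week window:

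| Scenario | p+ | p− | H = 5 | H = 10 |
|---|---|---|---|---|
| Persistent, 10% positive, onset 2 weeks | 0.046 | 0.080 | 1.184/1.320 = 0.90 | 1.414/1.720 = 0.82 |
| Persistent, 10% positive, onset 8 weeks | 0.020 | 0.082 | 1.080/1.328 = 0.81 | 1.180/1.738 = 0.68 |
| Persistent, 30% positive, onset 16 weeks | 0.013 | 0.092 | 1.052/1.368 = 0.77 | 1.117/1.828 = 0.61 |
| 12-week positivity, 10% positive, onset 2 weeks | 0.144 | 0.075 | 1.576/1.300 = 1.21 | – |

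The first and third rows are the ends of the persistent range: 0.77 to 0.90 at H = 5 and 0.61 to 0.82 at H = 10. At H = 2 that range is 0.93 to 0.97.

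The direction can change:

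- Constant risk (H = 1): the formula gives 1.00 whatever the shares.
- Lower early risk (H = 0.5), persistent positivity: 1.02 to 1.04.
- 12-week positivity, onset 2 weeks, H = 5 over a 16-week window: 2.08.
- 12-week positivity, onset 8 weeks, H = 5: 0.91 for a 4-week window, 1.34 for a 16-week window.
- A quarter of patients starting ixekizumab at rescue (persistent, 10% positive, onset 8 weeks): 0.81 at H = 5 and 0.68 at H = 10, almost the same as without rescue starters.

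**Stratified estimator.** In band k, let a and b be events in greater- and lesser-status time, T1 and T0 those times, and T = T1 + T0. The Mantel-Haenszel rate ratio is Σ(a·T0/T) / Σ(b·T1/T). With seven fine bands (edges at 1, 2, 4, 8, 16 and 28 weeks) it was 1.00 in every scenario above. With three bands (0–4, >4–16, >16 weeks) it is exactly 1.00 only when the risk changes at a band edge. With smoothly declining risk it was 0.96 to 1.03. With an abrupt change inside a band (high-risk window of 1, 2, 8 or 12 weeks) it was 0.90 to 1.00 for persistent and 0.85 to 0.99 for 12-week positivity.

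**The case against.** The best counter-argument is against a stronger reading. A reader might infer that antibody-positive time is late by construction, so antibodies must look protective. The SAP does not build that. Its rule back-dates positivity to the previous sample, or to the first dose when the first postbaseline sample is positive. A placebo patient rescued at Week 36 is next scheduled for sampling at Week 52. A positive result there makes all 16 weeks positive from the first ixekizumab dose. Patients can also return to lesser status. The direction therefore depends on facts the documents do not give.

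A reader might also take the bracketing rule itself as a bias. The same rule assigns both events and time, and at constant risk the ratio stays at 1.00.

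The summary's role is modest too. It follows a patient-level summary, by-patient listings come after it, and nothing calls it the trial's main antibody safety analysis. SAP 6.13.3.1 also lets a program safety analysis plan supersede special-topic analyses. That plan is not among the documents, so a time split there cannot be excluded.

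Sparse data are a fair objection. Take about 200 patients randomised to ixekizumab, a full year each and median onset 8 weeks. Greater-status time in Weeks 0–4 is then 200 × 0.082 × 0.020 = 0.3 patient-years at 10% positive, or 200 × 0.242 × 0.019 = 0.9 at 30%. This is repeated for three TE-ADA variables.

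These points limit the claim and its weight. They do not remove the missing time split.

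**Conclusion.** The point holds in a limited form. The planned rates confound TE-ADA status with time on drug, and nothing in the protocol or SAP separates the two. With no antibody effect, the crude ratio ran from 0.61 to 2.08 over the scenarios examined, and was 1.00 under constant risk. Those figures rest on assumed TE-ADA incidence, onset, persistence and event timing. They show what could happen, not what will.

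The documents do not support a claim that the bias is protective, or that it is certain to occur. This is a descriptive secondary safety summary. No efficacy result, hypothesis test or type I error rate depends on it. The change is worth considering because it is cheap and makes the output easier to interpret.

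**What to change.** In SAP 6.13.8.2.3, keep the crude rates. Add events, patient-years and rates by TE-ADA status within bands of time since first ixekizumab injection: 0–4, >4–16 and >16 weeks. Start the clock at the first rescue dose for patients randomised to placebo. Use a band-stratified Mantel-Haenszel rate ratio with a confidence interval as the summary comparison. One patient can contribute several events, so the interval should allow for clustering by patient. State in the text that the crude rates may be biased in either direction.

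The cost is SAP wording and one further split of data already collected. Some bands will be sparse, the interval will be wider, and for rare event types the ratio may not be estimable; the banded counts then stand alone. Some residual bias remains if risk changes within a band. Where the crude ratio happens to sit near 1, as in one 12-week-positivity scenario (0.997), three coarse bands can be slightly further from 1. If counts allow, splitting the first band at Weeks 1 and 2, where samples are scheduled for randomised patients, is a useful sensitivity analysis.
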